9.2.9 Early Study Termination

The sponsor can decide at any time to discontinue the study for any reason. Investigators will be informed of the decision. Ethics committees and competent authorities will also be informed if required by local regulations.

9.3 Variables

Only available evaluations as decided by the investigator based on local clinical practice will be collected in the study. Where there are no data to report, this will be indicated in the applicable section(s) of the electronic case report form (eCRF). See Table 1 for the schedule of assessments to be reported.

9.3.1 Demographic and Baseline Characteristics

- Baseline demography: year of birth, gender;
- Use of tobacco, occupational status, sick leave status;
- Presence of significant medical history including hypertension, diabetes, hypercholesterolemia, gastrointestinal (GI) diseases (e.g. inflammatory bowel disease), complication from prior GI surgery, dermatologic diseases, endocrine diseases, thromboembolism, myocardial infarction, stroke, risk of severe bleeding, renal and hepatic function impairment;

- History and baseline characteristics of RCC including: date of first diagnosis, stage at
 first diagnosis, stage at initiation of cabozantinib, histology, number and locations of
 metastatic sites, risk group category (International Metastatic Renal Cell Carcinoma
 Database Consortium (IMDC) [11] and MSKCC (Memorial Sloan Kettering Cancer
 Center) scores [12]);
- Previous systemic treatment for RCC including surgery of the primary tumour and of
 metastatic sites, type and number of systemic treatment lines for advanced disease
 including date of first and last dose, reason for discontinuation, best response, time to
 progression;
- Baseline clinical parameters (Eastern Cooperative Oncology Group (ECOG) performance status, weight, height, blood pressure) and electrocardiograms (ECGs); If clinically significant abnormal ECGs findings, as assessed by the investigator, are observed, further details will be collected (ie, heart rate, RR, PR, QRS, QT, and QTc durations).
- Planned frequency of radiological assessments during cabozantinib treatment.

9.3.2 Cabozantinib Pattern of Use

- Date of cabozantinib initiation, line of treatment, cabozantinib starting dose and schedule, date of the last dose of cabozantinib, any modification in the dose (reduction, increase, temporary interruption or discontinuation) with date and reason for the modification and schedule;
- Concomitant radiotherapies;
- Systemic therapy planned following cabozantinib discontinuation.

9.3.3 *Safety*

- During each data reporting period after Day 1 until the end of the study: clinical parameters (ECOG performance status, weight, blood pressure) and clinically significant results observed, as assessed by the investigator, for clinical laboratory tests and ECGs. Any clinically significant abnormality observed for laboratory tests and ECGs will be reported as AEs or SAEs. The investigator assessment of ECG findings (normal/abnormal) will be recorded. In case of clinically significant abnormal ECG findings, the investigator will report heart rate, RR, PR, QRS, QT, and QTc durations. In case of clinically significant abnormal laboratory parameters, the corresponding abnormal values will be reported in the AE Form in the eCRF.
- Occurrence of all serious and nonserious AEs.

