9.2.6 Study Schedule

The schedule of assessments to be reported is presented in Table 1.

In this noninterventional study, cabozantinib is to be administered as directed by the investigator according to the study site's usual clinical practice. The physician should refer to the Cabometyx TM SmPC for any information on the treatment prescribed.

Only available evaluations as decided by the investigator based on local clinical practice will be collected in the study. The most recent assessments available before each visit (including the inclusion visit if applicable) will be reported for 12-lead electrocardiograms (ECGs) and radiographic tumour assessments.

PAGE 26 OF 58

 Table 1
 Schedule of Assessments to be Reported

	Inclusion visit/ Treatment initiation Visit 1a	Visit 2 ^a	Visit 3 ^a	Visit 4 ^a	Visit 5 ^a	Visit 6ª	Visit 7ª	Visit 8ª	End of study visit Visit 9 ^a
Data reporting period (1 month=30 days)	D1	From D2 up to D30	Any time point from D31 up to D60	Any time point from D61 up to D90 (Month 3)	Any time point during Month 4 or Month 5	Any time point during Month 6 or Month 7	Any time point during Month 8 or Month 9	Any time point during Month 10 or Month 11	Any time point after Month 11 ^b
Assessments									
Signed informed consent	X								
Eligibility criteria	X								
Demographics, tobacco, occupational status, sick leave status	x								
Medical history, RCC cancer history and previous anticancer therapy	Х								
Planned frequency of radiological assessments	X								
ECOG performance status, height ^c , weight, vital signs	X	X	X	X	X	X	X	Х	X
12-lead ECG ^d	As available ^e	ECG performed according to local standards of care as clinically indicated ^f							
Clinical laboratory tests by local laboratory ^d		Clinical laboratory test to assess safety performed according to local standards of care as clinically indicated ^f							
Radiographic tumour assessment	As available ^e	Radiographic assessment performed according to local standards of care as clinically indicated ^f							
Concomitant medication	X	X	X	X	X	X	X	X	X
Radiotherapy/surgery	X ^g	X	X	X	X	X	X	X	X
Adverse events	X	X	X	X	X	X	X	X	X
Dose and schedule of cabozantinib prescribed	X	Х	x	X	X	Х	X	х	x^{h}
Cabozantinib dose modifications		X	X	X	X	X	X	X	$\mathbf{x}^{\mathbf{h}}$
Health care resource utilisation	X	X	X	X	X	X	X	X	x

PASS PROTOCOL: FINAL V 3.0: 21 JULY 2017 PAGE 27 OF 58

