	Inclusion visit/ Treatment initiation Visit 1a	Visit 2ª	Visit 3ª	Visit 4ª	Visit 5ª	Visit 6ª	Visit 7ª	Visit 8ª	End of study visit Visit 9 ^a
Data reporting period (1 month=30 days)	D1	From D2 up to D30	Any time point from D31 up to D60	Any time point from D61 up to D90 (Month 3)	Any time point during Month 4 or Month 5	Any time point during Month 6 or Month 7	Any time point during Month 8 or Month 9	Any time point during Month 10 or Month 11	Any time point after Month 11 ^b
Assessments									
Study discontinuation or completion form		In case of	In case of permanent treatment discontinuation (approximately 30 days after the last dose of cabozantinib) i					cabozantinib) i	х

Abbreviations: AE=adverse event, D=day, ECG=electrocardiogram, ECOG=Eastern Cooperative Oncology Group, eCRF=electronic case report form, RCC=renal cell carcinoma, SAE=serious adverse event

- a. Visits will take place according to the study site's clinical practice. The investigator will report data for study endpoint assessments during each data reporting period. Only available evaluations as decided by the investigator based on local clinical practice will be collected. Where there are no data to report, this should be indicated in the applicable section(s) of the eCRF. In the case of more than one visit occurring during the data reporting period, the visit closest to the end of the period should be used for reporting purposes.
- b. The closest visit to Month 12 should be recorded as End of study Visit
- c. Height will be recorded at Visit 1 only.
- d. Any clinically significant abnormal value observed for laboratory tests and ECGs will be collected and reported as AEs or SAEs
- e. The most recent evaluations performed before initiation of treatment.
- f. The most recent assessment available before each visit.
- g. Only concomitant radiotherapy will be collected (i.e., prior radiotherapy will not be collected).
- h. If applicable
- i. In case of permanent treatment discontinuation between Visit 2 and Visit 8, the next visit should be completed along with the Study discontinuation form, approximately 30 days after the last dose of cabozantinib.

PAGE 28 OF 58

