9.7.2.4 Safety Evaluation

All safety data will be included in the subject data listings using the Safety population. Analyses and summary tables will be presented by therapy line and in total based on the Safety population and also on the Primary Safety population.

All AEs will be coded according to the Medical Dictionary for Regulatory Activities (MedDRA) and will be classified by MedDRA preferred term (PT) and system organ class (SOC). Adverse event listings will be presented by subject, SOC and PT.

The incidence of all reported AEs, TEAEs, SAEs, and treatment-emergent serious and nonserious AEs will be tabulated separately. In addition, summary tables for TEAEs will be presented by maximum intensity and drug relationship. Treatment emergent AEs associated with dose modification (temporary interruption, reduction or discontinuation) of study medication and TEAEs leading to cabozantinib temporary dose interruption, reduction or discontinuation will also be summarised separately.

A TEAE is defined as any AE that occurs during the administration of cabozantinib if:

PAGE 33 OF 58

- It was not present prior to receiving the first dose of cabozantinib; or
- It was present prior to receiving the first dose of cabozantinib but the intensity increased during treatment with cabozantinib.

All TEAEs will be flagged in the AE listings.

Summary statistics (mean, median, SD and range, as appropriate) will be presented for ECOG performance status, vital signs (blood pressure), and weight at each assessment. Changes from baseline to each postbaseline assessment will be summarised similarly.

Counts and percentages of normal and abnormal ECG findings will be presented at each assessment. In addition, shift from baseline to postbaseline assessments in ECG findings will also be presented.

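### No pre-treatment laboratory result is collected, although any clinically significant result after Day 1 becomes an AE, so pre-existing abnormalities may be misclassified as treatment-emergent

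*Protocol*

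**What the plan says.** Four parts of the protocol bear on this point.

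- **Reporting rule.** Section 9.3.3 covers the time "During each data reporting period after Day 1 until the end of the study" and states "Any clinically significant abnormality observed for laboratory tests and ECGs will be reported as AEs or SAEs". The abnormal laboratory values go on the AE form in the eCRF. Footnote d of Table 1 repeats the rule.
- **Baseline collection.** Section 9.3.1 lists "Baseline clinical parameters (Eastern Cooperative Oncology Group (ECOG) performance status, weight, height, blood pressure) and electrocardiograms (ECGs"), together with medical and cancer history. It names no laboratory test. Section 9.2.6 says that the latest assessments available before each visit, including the inclusion visit where applicable, "will be reported for 12-lead electrocardiograms (ECGs) and radiographic tumour assessments". Laboratory tests are not in that sentence.
- **Table 1.** At Visit 1 the ECG and radiographic rows are marked as available, with footnote e: "The most recent evaluations performed before initiation of treatment". The laboratory row carries only the entry for later visits, "Clinical laboratory test to assess safety performed according to local standards of care as clinically indicated".
- **Treatment-emergent rule.** Under section 9.7.2.4 an AE during cabozantinib administration is treatment-emergent if it was not present before the first dose, or if "It was present prior to receiving the first dose of cabozantinib but the intensity increased during treatment with cabozantinib".

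**The concern.** The treatment-emergent rule compares the state on treatment with the state before the first dose. For laboratory abnormalities the plan collects the first and not the second. Every subject has had prior VEGF-targeted therapy, and section 9.3.1 itself expects histories of renal and hepatic impairment, diabetes and endocrine disease, so some subjects may well start with abnormal results.

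If such a result is first noted in the study data at an on-treatment test, it may enter the tables as a treatment-emergent event. Describing all treatment-emergent serious and nonserious AEs is a secondary objective of this post-authorisation safety study. The likelier direction of error is overstatement of laboratory events. A statistical analysis plan cannot repair this later, because it cannot recover values that were never recorded.

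**Working it through.** The protocol gives no figure on this point, so the check sets the sections against each other.

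**Step 1: is a pre-dose laboratory result collected anywhere?** The Visit 1 laboratory cell looks empty in the extracted Table 1, which alone would be weak evidence. The prose of sections 9.3.1 and 9.2.6 independently agrees with it. Footnote f of Table 1, on the most recent assessment before each visit, is attached to the laboratory entry for later visits, and section 9.3.3 keeps only clinically significant results. It does not supply a baseline.

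**Step 2: does the reporting rule exclude pre-existing findings?** Section 9.3.3 and footnote d cover any clinically significant abnormality. Section 11.1.1 describes an AE as a new condition or the worsening of an existing one, but then also includes abnormal investigation results associated in time with use of the product. An investigator could therefore report a stable, long-standing abnormality and be following section 9.3.3 to the letter.

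**Step 3: what else records the state before the first dose?**

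| Source | What it gives | What it leaves open |
|---|---|---|
| AE collection from consent (section 11) | AEs before the first dose | Section 9.2.7 places inclusion and treatment initiation together on Day 1, so this window can be close to nil |
| AE start and end dates (section 9.8.3) | An onset test against the first-dose date | No instruction to look back at earlier results when dating onset |
| CTCAE grade (section 11.3.2) | Intensity of the reported AE | No grade before the first dose unless a pre-dose AE was recorded |
| Medical history (section 9.3.1) | Presence of significant conditions | No laboratory value and no grade |

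**Step 4: apply the treatment-emergent rule to the possible cases.**

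| Laboratory abnormality | Result under section 9.7.2.4 |
|---|---|
| Absent before the first dose, appears on treatment | Correctly treatment-emergent, but not verifiable against a value |
| Present before, recorded as a pre-dose AE, with grade | Both tests can be applied |
| Present before, recorded as medical history only | Presence is known; an increase in intensity cannot be verified |
| Present before, in neither record, stable | Depends on how the investigator dates onset; may be counted as treatment-emergent |
| Present before, in neither record, worsened | Treatment-emergent in either case, but the increase cannot be verified |

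Misclassification arises mainly in the fourth case. The third and fifth are failures of verification.

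**Step 5: does it reach the primary endpoint?** Section 9.7.2.5.1 counts subjects with a dose modification due to an AE on the investigator's decision. The treatment-emergent flag is not part of that definition, so the primary proportion and the sample size built on it are unaffected.

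**The case against.** The strongest reply is that the rule in section 9.7.2.4 is written on the AE and its intensity, not on a laboratory value. AE dates, the date of cabozantinib initiation and CTCAE grades are all recorded. Clinical significance is the investigator's judgement, made with the subject's records at hand, and medical history covers many conditions that underlie laboratory abnormalities. Collecting only what local practice provides is a declared design choice, and its limits are acknowledged in section 9.9. The derivation rule and the table layout belong to a statistical analysis plan, which is not shown, and the AE form is not shown either.

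Much of this stands. A reader might infer that treatment-emergent status cannot be derived at all for laboratory events, or that pre-existing abnormalities are counted as treatment-emergent by rule. The protocol supports neither reading: the onset test is available from dates, and no sentence says that a known earlier abnormality counts as emergent.

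A reader might also extend the point to QTc, because under section 9.3.1 "further details will be collected (ie, heart rate, RR, PR, QRS, QT, and QTc durations") only when the baseline ECG was clinically significant. That does not follow. If the baseline ECG was not clinically significant, a later clinically significant one is new under the first limb of the rule. If it was, the intervals are recorded. Section 9.7.2.4 plans only normal/abnormal counts and shifts, not an analysis of QTc change.

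What the reply does not remove is the missing comparator. Nothing in the protocol requires a look-back at earlier results, and a monitor or analyst could not check one from the scheduled data. Using only available evaluations is no reason to leave laboratory tests out, since the same convention is already applied before treatment to ECG and imaging.

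**Conclusion.** The point holds as a risk of misclassification and a loss of verification. It is limited to laboratory abnormalities that pre-date treatment and were not captured with enough detail as history or as a pre-dose AE. It touches the laboratory entries in the descriptive treatment-emergent tables.

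Its size cannot be computed: the protocol gives neither the frequency of such abnormalities before treatment nor the share that would escape the other records. The conclusion rests on two assumptions: that the Visit 1 laboratory cell is empty as read, which sections 9.3.1 and 9.2.6 support, and that the AE form does not already ask for a pre-dose value. It is a worthwhile, inexpensive improvement and does not undermine the study's main result.

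**What to change.** 1. In sections 9.3.1 and 9.2.6 and the Visit 1 laboratory cell of Table 1, add laboratory tests as available (most recent before initiation of treatment). At minimum, have the AE form carry, for each laboratory AE, the last pre-dose value of the same parameter and its date, or a statement that none is available.
2. Align section 9.3.3 and footnote d with section 11.1.1, so that the laboratory findings to be reported are those that are new or worsened.
3. State that a laboratory AE counts as treatment-emergent only if it is new or of higher grade than the pre-dose value, and show laboratory AEs with no pre-dose value separately. The detail of this step can sit in the statistical analysis plan.

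The values come from existing records and no extra tests are needed, so the study stays noninterventional. The cost is a small group of eCRF fields and modest data entry. Some pre-dose values will be unavailable, which is why the separate display is needed.

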9.3.4 Effectiveness

• Date of clinical and radiographic progression or death, and overall response (based on Response Evaluation Criteria In Solid Tumours (RECIST) 1.1 [10]) as per investigator assessment.

9.3.5 Health Care Resource Utilisation During Treatment with Cabozantinib

- Assessment of health care resource utilisation associated with the prophylaxis or management of treatment-related AEs (as assessed by the investigator as certain, probable, possible or unlikely) during the treatment period:
 - hospitalisation
 - surgical procedures
 - emergency room visits

PAGE 30 OF 58

- intensive care unit stays
- concomitant medications (initiation or change to manage AEs)
- physician visits and homecare visits by nurse
- unplanned laboratory tests.

9.4 Data Sources

Source documents will include medical records and workup results (refer to Section 9.8.3 for definitions of source data and source documents). The source data will be collected by the investigator in the subject file and captured in an eCRF.

9.5 Study Size

The sample size is based on the primary endpoint which is the proportion of subjects with dose modifications due to AEs based on the investigator's decision (temporary interruption, dose reduction or discontinuation) assessed for each line of treatment (second line therapy or third and later line therapy). In the open-label METEOR Study, any dose reduction due to an AE occurred in 59.8% of subjects and the study drug was interrupted in 70% of subjects. Overall, at least one dose modification (i.e. reduction or interruption) was reported for 76% of subjects treated with cabozantinib. The rate of treatment discontinuation due to an AE was 9.7% for subjects treated with cabozantinib.

Assuming a dose modification proportion of 75%, a sample size of 289 subjects is required to estimate a 2-sided 95% level of confidence of the dose modification proportion with a precision of $\pm 5\%$. To have a precision of at least 5% in second line therapy and third and later line therapy, a minimum of 289 subjects must be included in each line of treatment (second line and third and later line).

Assuming that up to 15% subjects will start the treatment with cabozantinib using scheduled regimens different from the recommended regimen at initiation (60 mg/day) [8, 9], the total included population will represent 680 subjects.

The recruitment of subjects in the concerned subgroup will be closed as soon as the 340 subjects are reached.

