9.7 Data Analysis

9.7.1 Analysis Population Definitions

The following populations will be used during the statistical analyses:

- **Included population:** all subjects who signed the informed consent form (ICF);
- Full Analysis Set (FAS): all included subjects who have taken at least one dose of cabozantinib;
- **Safety population:** all included subjects who have taken at least one dose of cabozantinib and have a follow-up of safety;
- **Primary Safety population:** all subjects from the Safety population who started cabozantinib at the prescribed recommended dose.

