9.7.2.5 Endpoints and Evaluations

9.7.2.5.1 Primary Endpoint and Evaluations

The primary endpoint is the proportion of subjects with dose modifications due to AEs based on the investigator's decision (temporary interruption, dose reduction or discontinuation).

The primary analysis of the primary endpoint will be summarised descriptively for each line of treatment (second line or third and later line) and in total with their associated 2-sided 95% CIs based on the Clopper Pearson method using the Primary Safety population.

The impact of missing data on the analysis of the primary endpoint has been assessed. The precision of the proportion of subjects with dose modification due to AE has been calculated on different scenarios:

% of missing data	Number of evaluable subjects[a]	Precision[b]
5%	274	5.1%
10%	260	5.3%
15%	245	5.4%
20%	231	5.6%

- a From 289 subjects per line of treatment of the Primary Safety population
- b For a 95% CI and a proportion of subjects with dose modification of 75%

A proportion of missing data (ie, dose modification of cabozantinib due to AE) up to 20% is deemed acceptable in terms of precision of the estimation, meaning that, a proportion of more than 20% of missing data might impact the ability to assess the primary endpoint.

The proportion of missing data will be evaluated at time of the progress report and at time of the interim and final analyses.

A secondary analysis of the primary endpoint will be performed in a similar way and using the Safety population.

The proportion of subjects with dose modifications due to AEs related to cabozantinib (assessed by the investigator as certain, probable, possible or unlikely) will be described for the Safety population and for the Primary Safety population.

PAGE 34 OF 58

Additionally, this analysis will be repeated per AE relationship categories (certain/probable/possible/unlikely/not related/unassessable) (see definitions in Section 11.3.1).

The data for the primary endpoint will be listed using the Safety population.

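### The ±5% precision at 289 per line and the missing-data precision table are Wald figures, while the primary interval is Clopper-Pearson and is slightly wider

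*Protocol*

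**What the plan says.** Protocol Section 9.5, repeated in the Abstract under Study Size, sets the size per line of treatment: "Assuming a dose modification proportion of 75%, a sample size of 289 subjects is required" and the purpose is "to estimate a 2-sided 95% level of confidence of the dose modification proportion with a precision of" ±5%. The same target is then applied to each subgroup, and 289 becomes a floor there: "a minimum of 289 subjects must be included in each line of treatment (second line and third and later line". The section names no interval method. The only inflation is for up to 15% of subjects starting on a regimen other than 60 mg/day, which gives 680 in total, 340 per line. Recruitment then stops: "The recruitment of subjects in the concerned subgroup will be closed as soon as the 340 subjects are reached".

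Section 9.7.2.5.1 specifies that the primary endpoint is reported per line and in total "with their associated 2-sided 95% CIs based on the Clopper Pearson method using the Primary Safety population". The same section tabulates precision under 5, 10, 15 and 20% missing data as 5.1, 5.3, 5.4 and 5.6%. Its footnote gives the starting point: "From 289 subjects per line of treatment of the Primary Safety population". Up to 20% missing is declared acceptable for precision.

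Section 9.7.1 defines the Included population as "all subjects who signed the informed consent form (ICF"). The Primary Safety population additionally requires at least one dose, safety follow-up and a start at the recommended dose.

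**The concern.** The precision statement and the analysis refer to different intervals. A Clopper-Pearson interval is wider than a Wald interval at these sample sizes and is asymmetric around 75%. If 289 was derived from the Wald formula, the interval that will be reported is wider than the one used to justify the study.

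The study tests no hypothesis, so precision is the only statistical justification for 680 subjects. The judgement that 20% missing data is tolerable also rests on the tabulated half-widths. A second question is whether the step from 289 to 340 leaves anything for subjects who never take a dose, have no safety follow-up or lack endpoint data.

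**Working it through.** **Inputs.** p = 0.75, two-sided 95%, target half-width d = 0.05, 289 per line, up to 15% off-regimen, 340 per line (Section 9.5); Clopper-Pearson, and evaluable numbers 274, 260, 245 and 231 (Section 9.7.2.5.1).

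**1. Reproduce the plan's figures.** Wald: n = z²·p(1−p)/d² = 1.96² × 0.75 × 0.25 / 0.05² = 288.1, rounded up to 289. Inflation: 289/0.85 = 340 per line, 680 in total. Both stated figures reproduce.

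**2. Reproduce the table.** The Wald half-width is 1.96 × √(0.1875/n). It gives 5.13, 5.26, 5.42 and 5.58% for n = 274, 260, 245 and 231. Rounded, these are the printed 5.1, 5.3, 5.4 and 5.6%, so the table is Wald throughout.

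**3. Compute the specified interval.** The Clopper-Pearson limits are the 2.5% quantile of Beta(x, n−x+1) and the 97.5% quantile of Beta(x+1, n−x), with x = 0.75n (not always a whole number). Half-width = (upper − lower)/2; lower arm = 0.75 − lower limit.

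| Missing | Evaluable n | Protocol | Wald | Clopper-Pearson half-width | Lower arm |
|---|---|---|---|---|---|
| 0% | 289 | 5% | 4.99% | 5.15% | 5.41% |
| 5% | 274 | 5.1% | 5.13% | 5.29% | 5.56% |
| 10% | 260 | 5.3% | 5.26% | 5.43% | 5.72% |
| 15% | 245 | 5.4% | 5.42% | 5.60% | 5.91% |
| 20% | 231 | 5.6% | 5.58% | 5.77% | 6.10% |

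A whole-number check agrees: 217/289 (75.1%) has limits of 69.7% and 80.0%, a half-width of 5.14 points.

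**4. Number needed on the Clopper-Pearson basis.** The smallest n with a half-width of 5.0 points or less at 75% is 306. Requiring the lower arm alone to stay within 5 points would take 335, but that is stricter than anything the protocol asks.

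**5. Room in the inflation.** 340 × 0.85 = 289 exactly. At the full 15% off-regimen rate there is no margin for untreated subjects, absent safety follow-up or missing endpoint data. The rate is a ceiling, though. If all losses together are 10%, 340 × 0.90 = 306 remain and the half-width is 5.00%; with no loss at all, n = 340 gives 4.74%.

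**6. Dependence on the observed proportion.** At n = 289 the half-width is 5.02 points for 222/289 (76.8%) and 4.995 points for 223/289 (77.2%), so it falls below 5.0 from about 77.2% upward. At 76%, the rate the protocol cites from the pivotal trial, it is 5.08 points.

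**The case against.** The strongest reply is that the difference is too small to matter. The shortfall at 289 is 0.15 points, no success criterion depends on it, and the coverage of the reported interval is unaffected. That stands, and it keeps the severity low.

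A reader might infer that the design cannot deliver ±5%, or misses it even with perfect data. The documents do not support that. The 289 already assumes the full 15% loss, 306 or more evaluable out of 340 would meet the target, and so would an observed proportion of about 77.2% or more at 289.

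A reader might also infer that missing data were overlooked, or that the table contradicts Section 9.5. Neither follows. Section 9.7.2.5.1 sets out the loss of precision from 5 to 20% missing, accepts it, and has the missing proportion re-evaluated at the progress report and at the interim and final analyses. The table is a scenario for fewer evaluable subjects; the target in Section 9.5 is stated for 289. Not raising the sample size for missing data is a disclosed choice.

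The table is also already based on the right population: its footnote starts from the Primary Safety population, which Section 9.7.1 limits to treated subjects with safety follow-up who started at the recommended dose. Losses from untreated subjects may be few, since the decision to treat precedes inclusion and Visit 1 is also treatment initiation; the protocol gives no rate.

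What remains after all this is the mismatch of method. It affects the headline precision and every row of the table.

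**Conclusion.** The point holds in a limited form. The 289 for ±5% and the four tabulated precisions are Wald values, while the specified primary interval is Clopper-Pearson. At the protocol's assumed 75%, the half-width is 5.15 points at 289 evaluable and 5.3 to 5.8 points across the missing-data scenarios, about 0.15 to 0.2 points wider than stated. Meeting 5.0 points at 75% takes about 306 evaluable per line.

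If off-regimen starts reach the 15% ceiling, any further loss takes the evaluable number below 289; the protocol discloses the effect of missing data and accepts it up to 20%. The result rests on p = 0.75 and on reading precision as half the interval width. Severity is low: the stated precision becomes slightly less favourable, and the study's estimates and reported intervals are as planned.

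**What to change.** In Section 9.5 and the matching Abstract text, replace the ±5% wording, and the sentence claiming a precision of 5% or better, with a statement that 289 evaluable subjects per line give about ±5.2% at 75% by the Clopper-Pearson method (lower arm about 5.4 points).

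In the Section 9.7.2.5.1 table, replace the precision column with 5.3, 5.4, 5.6 and 5.8% for 5, 10, 15 and 20% missing, add a 0% row (289 evaluable, 5.15%), and name the interval method in the footnote. Confirm that up to 20% missing is still acceptable at 5.8%.

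The cost is a wording change in the protocol. Neither the sample size, the recruitment cap nor the analysis method has to change.
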